Exclusion Criteria	
Medical History
 
Autoimmune
 
 1. Active autoimmune disease that has required systemic treatment in past 2 years. Replacement therapy (e.g., thyroxine, insulin, or physiologic corticosteroid replacement therapy for adrenal or pituitary insufficiency) is not considered a form of systemic treatment; 
Cardiac
 
 2. Congestive heart failure (New York Heart Association Class III to IV); 3. History or presence of an abnormal electrocardiogram (ECG) that, in the investigator's opinion, is clinically meaningful. Screening QTc interval > 480 milliseconds is excluded. In the event that a single QTc is > 480 milliseconds, the subject may enroll if the average QTc for the 3 ECGs is < 480 milliseconds. For subjects with an intraventricular conduction delay (QRS interval > 120 milliseconds), the JTc interval may be used in place of the QTc with sponsor approval. The JTc must be < 340 milliseconds if JTc is used in place of the QTc. Subjects with left bundle branch block are excluded. 4. Uncontrolled or clinically significant conduction abnormalities (e.g., ventricular tachycardia on anti-arrhythmic are excluded), 1st degree AV block or asymptomatic LAFB/RBBB are eligible; 5. Uncontrolled, symptomatic ischemia within 6 months of first dose of study treatment or known myocardial infarction in the previous six months; 6. Patients with electronic pacemakers or defibrillators; 
Pulmonary
 
 7. Evidence of interstitial lung disease or any history of autoimmune pneumonitis including symptomatic and/or pneumonitis requiring treatment; 
Oncologic
 
 8. Any other current or previous malignancy within the past 2 years that, in the opinion of the Principal Investigator will interfere with study-specific endpoints; 
Infectious
 
 9. Evidence of significant active infection (e.g., pneumonia, cellulitis, wound abscess, etc.) requiring systemic therapy at time of study enrolment; 10. Patients with HBV surface antigen positive (HBSAg) must have AST and total bilirubin < 1.5 x ULN AND negative HBV RNA PCR OR on antivirals for HBV AND at least 8 weeks of prior anti-PD1 antibody therapy AND no history of AST or total bilirubin levels > 1.5 x ULN due to PD-1 antibody therapy. 11. Hepatitis C (HCV RNA [qualitative] is detected). 
Gastrointestinal

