3.3 Eligibility Criteria

Patients must have baseline evaluations performed prior to the first dose of epacadostat, pembrolizumab, or tavo-EP and must meet all inclusion and exclusion criteria. In addition, the patient must be thoroughly informed about all aspects of the study, including the study visit schedule and required evaluations and all regulatory requirements for informed consent. The written informed consent must be obtained from the patient prior to enrollment. The following criteria apply to all patients enrolled onto the study unless otherwise specified.

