3.3.1 Inclusion Criteria

Patient Characteristics

1. Age \geq 18 years old;
2. ECOG performance status 0-2;
3. Life expectancy of at least 4 months;

Disease Characteristics

4. Patients must have histological or cytological diagnosis of carcinoma of the head and neck that is not amenable to surgical resection or locoregional radiation therapy with curative intent;
5. At least one accessible lesion (AL) for intratumoral injection. An AL is defined as meeting the following criteria; (1) at least 0.3 cm x 0.3 cm in longest perpendicular diameters (2) in a suitable location for application of electroporation. Tumors invading the carotid artery or at other sites that the investigator believes to be at high risk of life-threatening hemorrhage should not be injected and these lesions may not be used to meet the inclusion criterion for injectable lesions
6. Measureable disease as defined by RECIST v1.1; at least one lesion where the longest perpendicular diameter is at least 1.0 cm by clinical measurement; or at least 1.0 cm by radiographic imaging for non-nodal lesions; at least 1.5 cm in short axis by radiographic imaging for malignant lymph nodes; If the biopsied lesions were previously irradiated, they must demonstrate either radiographic or pathological evidence of recurrent or residual disease. It is not necessary that this lesion is also an AL.
7. If patient has known brain metastases, they must have stable neurologic status following local therapy (surgery or radiation) for at least 4 weeks without the use of steroids or on stable or decreasing dose of ≤ 10 mg daily prednisone (or equivalent), and must be without neurologic dysfunction that would confound the evaluation of neurologic and other AEs (patients with a history of carcinomatous meningitis are not eligible);

Treatment History

8. Patients may have had prior chemotherapy or immunotherapy or radiation therapy. Any drug related adverse events identified during prior therapy must be well controlled (typically resolution to \leq grade 1, OR resolved upon investigator review prior to initiation of this therapy);
9. No systemic antineoplastic therapy may be received by the patient between the time of the biopsy and the first administration of study treatment;

Consent for Biopsies

10. Patient must agree to any protocol mandated biopsies of tumor (deemed accessible and safe for biopsy by the investigator's assessment) and they must allow acquired tissue to be used for biomarker analysis.

Fertility

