3.3.2 Exclusion Criteria

Medical History

Autoimmune

1. Active autoimmune disease that has required systemic treatment in past 2 years. Replacement therapy (e.g., thyroxine, insulin, or physiologic corticosteroid replacement therapy for adrenal or pituitary insufficiency) is not considered a form of systemic treatment;

Cardiac

2. Congestive heart failure (New York Heart Association Class III to IV);
3. History or presence of an abnormal electrocardiogram (ECG) that, in the investigator's opinion, is clinically meaningful. Screening QTc interval > 480 milliseconds is excluded. In the event that a single QTc is > 480 milliseconds, the subject may enroll if the average QTc for the 3 ECGs is < 480 milliseconds. For subjects with an intraventricular conduction delay (QRS interval > 120 milliseconds), the JTc interval may be used in place of the QTc with sponsor approval. The JTc must be < 340 milliseconds if JTc is used in place of the QTc. Subjects with left bundle branch block are excluded.
4. Uncontrolled or clinically significant conduction abnormalities (e.g., ventricular tachycardia on anti-arrhythmic are excluded), 1st degree AV block or asymptomatic LAFB/RBBB are eligible;
5. Uncontrolled, symptomatic ischemia within 6 months of first dose of study treatment or known myocardial infarction in the previous six months;
6. Patients with electronic pacemakers or defibrillators;

Pulmonary

7. Evidence of interstitial lung disease or active, noninfectious pneumonitis including symptomatic and/or pneumonitis requiring treatment;

Oncologic

8. Any other current or previous malignancy within the past 2 years that, in the opinion of the Principal Investigator will interfere with study-specific endpoints;

Infectious

9. Evidence of significant active infection (e.g., pneumonia, cellulitis, wound abscess, etc.) requiring systemic therapy at time of study enrolment;
10. Hepatitis B – Most NPC patients have been infected with hepatitis B (Cancer Epidemiol Biomarkers Prev. 2015. 24:1766-73, N = 711) and, therefore, the inclusion of healthy patients with a history of hepatitis B is a central part of this study. In addition, PD-1 antibodies have been proven to be safe in patients with active hepatitis and hepatocellular carcinoma (e. g. KEYNOTE 224). However, patients with HBV surface antigen positive (HBsAg) must have AST and total bilirubin < 1.5 x ULN AND:
 11. Negative HBV RNA PCR OR;

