 12. On antivirals for HBV AND at least 8 weeks of prior anti-PD1 antibody therapy AND no history of AST or total bilirubin levels > 1.5 x ULN due to PD-1 antibody therapy
 13. Hepatitis C (HCV RNA [qualitative] is detected).

Gastrointestinal

14. Presence of a gastrointestinal condition that may affect drug absorption. Administration of epacadostat through a feeding tube is permitted.

Medications / Medication Reactions

15. Patients receiving systemic steroid therapy for a chronic inflammatory condition. Topical steroids, nasal and inhaled steroids are permitted. Prednisone or equivalent ≤ 10 mg/day is permitted as hormone replacement; higher dosage prednisone should be stopped at least 14 days prior to C1D1;

16. Receipt of live attenuated vaccine within 30 days before the first dose of study treatment. Examples of live vaccines include, but are not limited to, the following: measles, mumps, rubella, chicken pox, yellow fever, rabies, *Bacillus Calmette-Guérin* (BCG), and typhoid vaccine. Seasonal influenza vaccines for injection are generally killed virus vaccines and are allowed; however, intranasal influenza vaccines (eg, FluMist[®]) are live attenuated vaccines and are not allowed.

17. Subjects receiving Monoamine Oxidase Inhibitors (MAOIs) or drug which has significant MAOI activity (meperidine, linezolid, methylene blue) within the 21 days before screening.

18. Any history of Serotonin Syndrome (SS) after receiving serotonergic drugs.

19. Use of any UGT1A9 inhibitor from screening through follow-up period, including the following: diclofenac, imipramine, ketoconazole, mefenamic acid, and probenecid.

20. Known allergy or reaction to any component of epacadostat, pembrolizumab, or tavo-EP formulation.

Laboratories

21. Screening Laboratory Abnormalities

- a. Absolute neutrophil count (ANC) $< 1.0 \times 10^9/L$.
- b. Platelets $< 75 \times 10^9/L$.
- c. Hemoglobin $< 9 \text{ g/dL}$ or $< 5.6 \text{ mmol/L}$ (transfusion is acceptable to meet this criterion).
- d. Serum creatinine $\geq 1.5 \times$ institutional upper limit of normal (ULN) OR measured or calculated creatinine clearance (glomerular filtration rate can also be used in place of creatinine or CrCl) $< 50 \text{ mL/min}$ for subjects with creatinine levels $> 1.5 \times$ institutional ULN.
- e. AST or ALT $> 2.5 \times$ institutional ULN.

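### Exclusion 7 contradicts itself: the synopsis bars any past autoimmune pneumonitis, Section 3.3.2 bars only active noninfectious pneumonitis, and nothing says which governs

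*Combined protocol and SAP*

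**What the plan says.** The pulmonary exclusion appears twice, each time as criterion 7.

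- Synopsis, Exclusion Criteria: "Evidence of interstitial lung disease or any history of autoimmune pneumonitis including symptomatic and/or pneumonitis requiring treatment".
- Section 3.3.2: "Evidence of interstitial lung disease or active, noninfectious pneumonitis including symptomatic and/or pneumonitis requiring treatment".

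The opening and closing words match. The middle differs in two ways: history against current activity, and autoimmune against noninfectious.

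Three other provisions bear on the point.

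- Inclusion 8 (Section 3.3.1, and the same in the synopsis) states "Patients may have had prior chemotherapy or immunotherapy or radiation therapy". It adds "Any drug related adverse events identified during prior therapy must be well controlled", and explains that this typically means grade 1 or lower, or resolved on the investigator's review.
- Section 3.3 introduces its list with "The following criteria apply to all patients enrolled onto the study unless otherwise specified".
- Table 4-5 (Section 4.3.3) sets the on-study response to pneumonitis. Grade 3 or 4 means permanent discontinuation of epacadostat and pembrolizumab. Grade 2 means interruption, with return allowed on improvement to grade 1 or lower. Discontinuation becomes permanent if the event has not resolved within 12 weeks of the last dose, or if steroids cannot be brought down to 10 mg of prednisone a day (or equivalent) in that time.

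**The concern.** An eligibility criterion should give one answer for one patient. Here a site working from the synopsis would turn away a patient with past autoimmune pneumonitis, and a site working from Section 3.3.2 would accept the same patient once the event had resolved. The trial is multicenter, so both decisions could be made.

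The patient in question is foreseeable. Prior immunotherapy is permitted, and Table 4-5 itself lists pneumonitis among the events to be managed on pembrolizumab and epacadostat. Both dose-expansion arms and the lead-in receive pembrolizumab; the lead-in and Arm A also receive epacadostat. If Section 3.3.2 is the text that sites follow, a person whose earlier pneumonitis was of a kind that ends treatment on this study could start the same class of drug again.

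**Working it through.** There is no figure to reproduce, because the point depends on no rate, error level or sample size. The check sets the two wordings side by side for each type of patient and then looks for anything that resolves the difference.

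**Step 1: apply each wording of criterion 7.**

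| Patient | Synopsis | Section 3.3.2 |
|---|---|---|
| Interstitial lung disease | Excluded | Excluded |
| Active autoimmune pneumonitis | Excluded | Excluded |
| Resolved autoimmune pneumonitis, no interstitial lung disease | Excluded | Not excluded |
| Active noninfectious pneumonitis that is not autoimmune, such as radiation pneumonitis | Unclear | Excluded |

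The third row is a direct conflict. The fourth is an ambiguity: the synopsis reaches that patient only if its closing phrase about symptomatic or treated pneumonitis is read more widely than the autoimmune events it follows.

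**Step 2: can *active* in Section 3.3.2 be read to cover a past event?** No. The closing phrase has no history element. Where Section 3.3.2 means history it says so, as in its serotonin syndrome criterion.

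**Step 3: does another criterion exclude the third-row patient?**

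- Inclusion 8 accepts earlier drug-related events once they are controlled or resolved, so it admits the patient.
- Exclusion 1 is limited to active autoimmune disease that needed systemic treatment in the past 2 years. It does not name pneumonitis or cover a resolved event.
- The steroid exclusion (criterion 15 in Section 3.3.2) concerns current treatment. It requires that "higher dosage prednisone should be stopped at least 14 days prior to C1D1", which a patient with a resolved event can meet.

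None closes the gap.

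**Step 4: is there a rule of precedence?** None is stated. The introduction to Section 3.3 applies its own list to all enrolled patients, which favours Section 3.3.2, the looser text on history.

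**Step 5: which past events would end treatment on this study?** By Table 4-5, all grade 3 or 4 events, and those grade 2 events that fail the 12-week conditions. Neither version of criterion 7 grades a past event, so under Section 3.3.2 any of these patients could enter once the event is no longer active, as far as this criterion goes.

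**The case against.** The best defence is that the body of a protocol governs its synopsis. On that view Section 3.3.2 is coherent: it agrees with inclusion 8 in accepting resolved drug-related events, and residual interstitial disease remains excluded. This stands as far as it goes. The fault is inconsistency between two places; the Section 3.3.2 sentence is not wrong taken alone. But the protocol does not state that rule, and adopting it makes the weaker safeguard the operative one without explanation.

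A second objection also stands in part. The synopsis says autoimmune, while Section 4.3.3 calls events caused by these drugs immune-related or immune-mediated. The conflict is certain only for autoimmune pneumonitis as worded. Including pneumonitis caused by earlier PD-1 therapy is a plausible reading, not a stated one.

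Three stronger readings are tempting and are not supported.

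- *Only past grade 3 or 4 events matter, so the criterion should be cut there.* The grade 2 row of Table 4-5 also leads to permanent discontinuation under its 12-week conditions, and neither version of criterion 7 uses a grade. Such a cut would be a third rule found in neither place.
- *The conflict affects all, or most, of the planned patients.* Criterion 7 is applied to everyone at screening, but the planned total is enrolment and does not count patients with past pneumonitis.
- *The hepatitis B item shows that Section 3.3.2 means to screen on past PD-1 toxicity and forgot the lung.* Its liver-history clause, "no history of AST or total bilirubin levels > 1.5 x ULN due to PD-1 antibody therapy", belongs to one route for patients positive for hepatitis B surface antigen who are on antivirals. It shows no general intention.

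**Conclusion.** The two current versions of exclusion 7 give opposite answers for a patient with resolved autoimmune pneumonitis. They also leave active non-autoimmune pneumonitis unclear under the synopsis. This should be corrected.

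The number of patients affected cannot be estimated, because the documents give no frequency of past pneumonitis. Nothing in the sample size, the two-stage rule or the analysis changes.

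The safety argument rests on two assumptions: that Section 3.3.2 is followed in practice, and that autoimmune includes immune-mediated events from earlier therapy. A reader might infer that enrolling such a patient breaches Table 4-5. It does not, because that table governs events that occur on study. It is relevant only as the protocol's own view of how serious such events are.

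**What to change.** Put one sentence, combining the two existing wordings, in both the synopsis and Section 3.3.2:

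> *Evidence of interstitial lung disease, any history of autoimmune (including immune-mediated) pneumonitis, or active noninfectious pneumonitis of any cause.*

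The amendment should say that the words in parentheses clarify the synopsis term.

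Until it is approved, tell sites to exclude a patient who meets either wording. Everyone enrolled on that basis satisfies both versions.

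The cost is one sentence in two places, through the ordinary amendment route in Section 12.4 (signature by the investigator, then approval by the protocol review committee and the IRB). Relative to Section 3.3.2, a few more patients with prior immunotherapy would be excluded.

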3.4 Schedule of Procedures and Observations

The study-specific assessments are detailed in this section and outlined in **Table 3-1: Study Calendar**. Screening assessments must be performed within 28 days prior to the first dose of investigational product unless otherwise noted. Any results falling outside of the reference ranges may be repeated at the discretion of the investigator. All on-study visit procedures are allowed **a window of ± 3 days** unless otherwise noted. Treatment or visit delays for public holidays or weather conditions do not constitute a protocol violation.

A written, signed, informed consent form (ICF) and a Health Insurance Portability and Accountability Act (HIPAA) authorization must be obtained before any study-specific assessments are initiated. A copy of the signed ICF will be given to the subject and a copy will be filed in the medical record. The original will be kept on file with the study records. Informed consent for specimens for Future Biomedical Research may also be obtained during screening and must be obtained prior to collection of all Future Biomedical Research specimens.

All patients who are consented will be registered in OnCore®, the UCSF Helen Diller Family Comprehensive Cancer Center Clinical Trial Management System (CTMS). The system is password protected and meets HIPAA requirements.

4 Treatment

Treatment will be administered on an outpatient basis.

4.1 Dose Escalation Schedule

The recommended starting dose of single agent epacadostat is 300 mg twice daily. The current study is designed to determine the MTD of epacadostat in combination with pembrolizumab and tavo-EP.

Table 4-1: Dose Escalation for epacadostat

Dose	N	Epacadostat(mg) (po BID) in 28 day cycles
-1	3	200 mg
0	3	300 mg
1	3	600 mg

Rationale for dose levels -1 to 1: The primary endpoint of the dose escalation safety run-in is to determine if epacadostat at 600 mg is a safe and tolerable dose in the combination of tavo-EP and pembrolizumab in patients with recurrent or metastatic squamous cell carcinoma of the head and neck with tumors.

The starting dose will be dose level 0. Dose level -1 may be selected if higher dosing cohorts are not tolerated.

Higher dose of epacadostat will be considered if no DLTs are seen at dose level 0. e.g. 300 mg bid.

4.2 Dose Expansion Schedule

Table 4-2: Dose Expansion Arms in both Stage 1 and 2

	Treatment Arms	N	Epacadostat	pembrolizumab	tavo-EP
Arm A	tavo-EP, pembrolizumab ad epacadostat	28*	MTD - as determine by dose escalation	200 mg via IV. Days 1 and 22 of each cycle for 6 weeks (42 days)	1/4 tumor volume at concentration of 0.5 mg/mL ¹ given intratumoral on Days 1, 5, 8 of each cycle for 6 weeks (42 days)
Arm B	tavo-EP and pembrolizumab	28			

*Patients in the dose escalation safety lead-in will have an opportunity to participate in Stage 1, Arm A per Investigator's discretion.

Rationale for cohort expansion: In the dose expansion cohorts, we will determine the tolerability of this combination, the recommended phase II dose (RP2D) and preliminary efficacy in 56 evaluable patients with recurrent or metastatic squamous cell carcinoma of the head and neck with tumors. Hence the cohort expansion warrants the confirmation of tolerability of this combination, was deemed safe will be pursued for further patients.

4.3 Dose Limiting Toxicity (DLT) and Maximum Tolerated Dose (MTD)

If DLT is encountered during the first cycle, the following rules (see table below) will be applied. If no DLT is encountered at a given dose level, escalation will be continued to the next higher dose level. If no DLT is found at the highest cohort, this cohort will be considered the recommended Stage 1 dose for epacadostat.

Table 4-3: Dose Escalation Decision Rules - DLT and MTD

Number of Patients with DLT at a Given Dose Level	Escalation Decision Rule
0 out of 3	Escalate dose to next higher dose level
1 out of 3	Enter at least 3 more patients at this dose level If 0 of these 3 additional patients experience DLT (1 of 6), proceed to the next dose level If 1 or more of the 3 additional patients suffer DLT (2 of 6), then dose escalation is stopped and this dose is declared the maximal administered dose (highest dose administered) Determination of the MTD will continue at the next lowest dose cohort, at which an additional 3 patients will be added, for a total of 6 (unless that cohort already has 6 patients)

≥ 2 out of 3	Dose escalation will be stopped This dose level is declared the maximum administered dose The next lower cohort will be expanded to 6 patients If < 1 experience DLT, this dose is the maximal tolerated dose (MTD)
≤ 1 out of 6 at highest dose level below the maximum administered dose	This is generally the recommended Phase 2 dose At least 6 patients must be entered at the recommended Phase 2 dose

4.3.1 Dose Limiting Toxicity

Adverse Events and other symptoms will be graded according to the NCI Common Terminology Criteria for Adverse Events Version 4.03 (NCI, CTC web site <http://ctep.info.nih.gov>).

A DLT will be defined as any one of the following adverse events occurring during Cycle 1 when association to therapy that is part of this study is related or possibly related:

1. Hematologic dose-limiting toxicity

- Grade 4 neutropenia lasting for ≥7 days in duration.
- Febrile neutropenia of any grade
- Grade 4 thrombocytopenia ($\leq 25.0 \times 10^9/L$) lasting for ≥7 days in duration.
- Grade 3 thrombocytopenia complicated by clinically significant bleeding and/or requiring platelet or blood transfusion

2. Non-hematologic dose-limiting toxicity

This will be defined as any Grade ≥3 non-hematologic toxicity, which is clinically meaningful and related with the specific **EXCEPTION** of:

- Any grade alopecia
- Grade 3 total hyperbilirubinemia if <35% is direct component
- Grade 3 transient ALT/AST elevation
- Grade 3 rash, nausea, vomiting or diarrhea for ≤ 3 days or is not properly managed with optimal supportive care
- Grade 3 lab abnormalities must be clinically significant, meaningful and dose related.

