Dose Escalation Safety Lead-In and Mid-Study Interim Safety Analysis	
Dose Escalation Safety Lead-In
 
1. If, at any time, 1 or more of the first 3 safety-evaluable patients experience grade 3 or higher treatment-associated adverse events within the first 30 days of initiation of treatment, then no further patients will be enrolled at the current dose level.2. After 6 patients have been enrolled on study, enrollment will be halted for 30 days for completion of the dose escalation lead-in safety analysis. If 0-1 patients experience grade 3 or higher treatment-associated adverse events within the first 30 days of initiation of treatment, then additional patients may be enrolled at the next dose level.3. If enrollment is halted at any time during the lead-in period due to treatment-associated adverse events, the UCSF DSMB will review all available safety data with the Principal Investigator. Based on this review, study discontinuation or reduction of the epacadostat dose may be recommended. No further patients will be enrolled on study without the approval of the DSMB. If the DSMB allows additional patients to enroll, the lead-in period will be repeated at the new dose level with a maximum of 6 additional patients enrolled prior to follow-up safety analysis. At the discretion of the DSMB, patients who are currently on study may continue treatment at the reduced dose level.4. Patients who discontinue treatment on study within 30 days of initiation of therapy for reasons other than treatment-associated toxicity will be deemed inevaluable for safety and replaced for safety analysis. 
Mid-Study Interim Safety Analysis (Stage 1)
 
Enrollment will also be halted for 30 days for interim safety analyses after a total of 30 safety-evaluable patients have initiated treatment on study in both Arms A and B. Patients who discontinue treatment on study within 30 days of initiation of therapy for reasons other than treatment-associated toxicity will be deemed inevaluable for safety and replaced for safety analysis. The study will be discontinued under the following circumstance:
 
1. On-study occurrence of 3 or more Grade 4 (life threatening) serious adverse events (SAEs) or deaths, which are deemed at least possibly related to the study agent.2. Based on the review of data the DSMB has serious concerns about the safety of patients on the study. In addition to stopping the study, the DSMB may recommend that the epacadostat dose for all patients be de-escalated for all current and future patients or cessation of further patient accrual.

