--	---

Duration of Therapy	
Dose Escalation Safety Lead-In Phase: 6 patients will receive triplet therapy for 30 days at Dose level 0. After 30 days of therapy, if those patients do not experience a DLT, an additional 6 patients will be enrolled at the next Dose level, Level 1 which will increase epacadostat to 600 mg for 30 days, tavo-EP and pembrolizumab will not be dose escalated. If no patients experience a DLT at 600 mg, that will be the dose level of epacadostat used in Stage 1, for both Arms A and B.
 
Dose Expansion Phase, Stage 1, Arm A: Patients will receive triplet therapy for 12 months or until the development of an unacceptable treatment associated toxicity or confirmed progression. After 12 months of therapy, patients will enter the follow-up phase for the next 24 months. Patients with disease progression during the follow-up phase will have access to 12 additional months of triplet therapy. Patients who are eligible for treatment on study but who have experienced regression of all previously accessible lesions may continue on pembrolizumab and epacadostat without tavo-EP.
 
Dose Expansion Phase, Stage 1, Arm B: Patients will receive combination therapy for 12 months or until the development of an unacceptable treatment associated toxicity or confirmed progression. After 12 months of therapy, patients will enter the follow-up phase for the next 24 months.
 
Dose Expansion Phase, Stage 2: Depending on the results of the clinical data in Stage 1, Stage 2 will enroll up to an additional 26 patients accordingly:
 
If there are at least ≥ 3 responses in 15 patients, in either Arms A or B, up to an additional 26 patients (13 patients in Arm A and 13 patients in Arm B) will be enrolled in the respective treatment arms.

Duration of Follow up	Patients will be followed at 3 month intervals for toxicity and radiographic imaging 1) until start of a new anti-cancer treatment, (2) until 30 days after documented disease progression, (3) until death, or (4) until 36 months from the initiation of treatment on study, whichever comes first. Each subject will be followed for overall survival until death, withdrawal of consent, or the end of the study, whichever occurs first.
Duration Of Study	Study accrual will be sufficient to assess the primary endpoint within 24 months from the time the study opens to accrual.

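### The bleeding/transfusion DLT line names Grade 3 thrombocytopenia only, so a transfused Grade 4 event under 7 days is literally not a DLT while the milder Grade 3 event is

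*Combined protocol and SAP*

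**What the plan says.** Section 4.3.1 defines a DLT as any one of a list of related or possibly related events in Cycle 1. Three entries matter here:

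- Grade 4 thrombocytopenia, with the condition "lasting for ≥7 days in duration". No bleeding or transfusion trigger is attached.
- "Grade 3 thrombocytopenia complicated by clinically significant bleeding and/or requiring platelet or blood transfusion", with no minimum duration.
- The general clause, "any Grade ≥3 non-hematologic toxicity, which is clinically meaningful and related", which has listed exceptions and is confined to non-hematologic toxicity.

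The DLT count feeds two sets of dose rules. In Table 4-3, 0 of 3 leads to "Escalate dose to next higher dose level", 1 of 3 adds at least 3 patients, 1 of 6 proceeds, and 2 of 3 or 2 of 6 stops escalation. The Synopsis (Duration of Therapy) works with 6 patients per level: "if those patients do not experience a DLT, an additional 6 patients will be enrolled at the next Dose level", and then "If no patients experience a DLT at 600 mg, that will be the dose level of epacadostat used in Stage 1".

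Separate lead-in rules count any Grade 3 or higher treatment-associated adverse event within 30 days, whether or not it is a DLT. The Synopsis lead-in item 1 closes a level to further enrollment if "1 or more of the first 3 safety-evaluable patients experience grade 3 or higher treatment-associated adverse events". Its item 2 says that with 0-1 such patients after 6, "then additional patients may be enrolled at the next dose level". Section 5.2 closes a level at 2 or more of the first 6.

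**The concern.** A toxicity definition should not count the milder form of an event and leave out the more severe form. Here the complication that makes Grade 3 thrombocytopenia dose-limiting, a transfusion or a significant bleed, loses that effect once the platelet count falls further to Grade 4. Grade 4 then depends on duration alone. Platelet transfusion is given to raise the count, so treating the patient may itself shorten the time at Grade 4 and keep the episode under 7 days.

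Two things are at stake: the DLT count that sets the epacadostat dose, and the handling of the patient concerned, because Section 4.3.2 allows dose modification in Cycle 1 only after a DLT.

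**Working it through.** The plan states no figure that depends on this line, and no sample size or power value changes. The check is to classify each case against Section 4.3.1 and carry the result into the dose rules.

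**Step 1: classification of related Cycle 1 events, read literally**

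| Thrombocytopenia | Complication | Duration | DLT? |
|---|---|---|---|
| Grade 3 | transfusion or significant bleed | any | Yes |
| Grade 4 | none | ≥7 days | Yes |
| Grade 4 | transfusion | ≥7 days | Yes, through duration only |
| Grade 4 | transfusion | <7 days | **No** |
| Grade 4 | significant bleed below Grade 3 | <7 days | **No** |
| Grade 4 | bleed itself Grade 3 or higher | <7 days | Can count under the non-hematologic clause |

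Rows 4 and 5 are more severe than row 1 but are not counted.

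**Step 2: effect of one uncounted event on the dose rules**

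| Setting | Count as written | Count if the event is included | Separate rule, within 30 days |
|---|---|---|---|
| Table 4-3, only event in 3 | 0 of 3: escalate | 1 of 3: add at least 3 | Synopsis item 1 halts; Section 5.2 does not (1 event, needs 2) |
| Table 4-3, plus one counted DLT in 6 | 1 of 6: proceed | 2 of 6: stop | Section 5.2 halts, unless the counted DLT is febrile neutropenia below Grade 3, which 4.3.1 admits at any grade |
| Table 4-3, only event in 6 | 0 of 6: proceed | 1 of 6: proceed | No change in decision |
| Synopsis Duration of Therapy, only event in 6 | no DLT: go to, or adopt, 600 mg | 1 DLT: text gives no rule | Synopsis item 1 halts only if the event is in the first 3; Section 5.2 does not |

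**Step 3: what the 30-day rules miss**

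Table 3-1 gives Cycle 1 as 42 days. The stopping rules cover 30 days, so 42 − 30 = 12 days (days 31-42) lie inside the DLT window but outside those rules. This matters only if the Table 4-3 decision waits for the end of Cycle 1. It disappears if the 28-day cycle mentioned in Table 4-1 is the one meant.

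Three exposed situations remain:
1. The event falls on days 31-42.
2. Section 5.2 alone governs a cohort of 3.
3. The Synopsis is read as requiring zero DLTs in 6.

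**Step 4: how often**

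Section 1.2 reports no Grade 4 thrombocytopenia in 96 patients on tavo-EP alone (Table 1-1), 22 on tavo-EP with pembrolizumab (Table 1-3), or 60 on epacadostat with pembrolizumab (no Grade 4 treatment-related event of any kind). That is 96 + 22 + 60 = 178 patients. None received the triplet, and epacadostat went no higher than 300 mg BID. The figures support calling the event rare but do not give a rate for this regimen.

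**The case against.** The strongest case on the other side has three parts.

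**Intent.** The authors very likely meant Grade 3 or higher. A patient who reaches Grade 4 may be seen at Grade 3 on the way down or up, and Section 11.3 has every grade change recorded, so an investigator could count the event under the existing line. This is reasonable but not secured by the text. The same section writes ≥3 for non-hematologic toxicity and admits febrile neutropenia of any grade, so Grade 3 alone reads as Grade 3. Nothing says that a complication arising at Grade 4 counts under the Grade 3 line.

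**Other safeguards.** Section 4.3.3 withholds all three agents for drug-related Grade 4 hematologic toxicity. Appendix 2 puts all adverse events before the DSMC Chair before escalation, and it treats an event in a gene therapy study as serious. These protections are real, but none adds the event to the DLT count.

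**Stopping rules.** Within 30 days these deal with most of the Table 4-3 cases. That stands, and it is the main reason the point is small.

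Three stronger readings are tempting and should be resisted:

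- A reader might infer that the gap readily sends the trial to too high a dose. Within 30 days, Synopsis item 1 bars enrollment after one such event in the first 3, and item 3 then requires DSMB approval for any further patient. Section 5.2 does the same at 2 of 6.
- A reader might infer that one DLT in 6 rules out 600 mg under the Synopsis. The text says what follows if there is no DLT. It does not say that this is the only route, and Table 4-3 lets 1 of 6 proceed.
- A reader might want to attach a probability to a missed event. The documents give no rate for it, and any assumed one would be arbitrary.

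**Conclusion.** The line is wrong as written, and the severity is minor. The inversion between Grade 3 and Grade 4 follows directly from Section 4.3.1, and no other provision repairs the DLT count. Its practical reach is confined to a rare event in the three exposed situations listed above. The second and third depend on which of the protocol's differing lead-in rules is taken to govern, and the first on a 42-day Cycle 1.

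The effect on the individual patient is real but also limited. An uncounted event does not open dose modification in Cycle 1 under Section 4.3.2, although treatment is withheld anyway. The later paragraph on dose modification versus interruption bars dose reductions altogether; if that paragraph governs, this consequence falls away.

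**What to change.** In Section 4.3.1, change Grade 3 to Grade ≥3 at the start of the bleeding/transfusion line and leave the rest of the line as it is. A transfused or significantly bleeding Grade 4 patient then counts at once, and the 7-day condition applies only to uncomplicated Grade 4 events.

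The cost is one symbol in an amendment, with no added patients, visits or analyses. The only downside is that a dose decision may become slightly more conservative.
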